Rural areas in the United States are increasingly impacted by HIV, tied to the ongoing opioid epidemic, growing stimulant use, and widespread drug injection. Kentucky (KY) is among seven states identified with heavy rural HIV burden and increasing rates of new HIV diagnoses attributable to injection drug use: in 2018, 36% of HIV-diagnosed women in KY had injection drug use as a transmission factor, as did 10% of men. Rural HIV outbreaks among people who inject drugs (PWID) have occurred recently in KY's neighboring states, including Indiana, West Virginia, and North Carolina. With increases in HIV transmission among PWID expected to continue, there is an urgent need to implement proven HIV prevention and harm reduction strategies for PWID in KY's rural areas.

Existing Knowledge

A key pillar of Ending the HIV Epidemic (EHE): A Plan for America is the prevention of new HIV infections through scale up of evidence-based interventions, including syringe service programs (SSPs) and Pre-exposure prophylaxis (PrEP). SSPs are a proven structural HIV prevention tool and are currently operational in 62 KY counties.

Research in KY's Appalachian region has demonstrated consistent use of rurally located SSPs by high-risk PWID, making SSPs a critical venue to scale delivery of comprehensive HIV prevention services in rural areas. While SSPs are increasing access to sterile injection equipment for rural PWID, several gaps remain in HIV prevention, including suboptimal uptake of HIV testing, inadequate syringe coverage, and low access to PrEP providers in rural communities.

Need for a Trial

The expansion of PrEP has been endorsed as a key strategy for impacting the course of the HIV epidemic, however, PrEP trials among PWID are largely absent from the literature, particularly in rural areas. Structural barriers to healthcare access, lack of providers, and inadequate infrastructure to deliver PrEP are challenges in many rural areas. In addition, PWID often have low PrEP knowledge, limited perception of risk, high HIV-related stigma, and other competing needs that act as barriers to PrEP uptake. This study will integrate PrEP education, screening, prescribing and monitoring within the SSP, a venue already routinely accessed by rural PWID, to reduce structural barriers to access to this evidence-based HIV prevention intervention through co-located comprehensive PrEP services.

6b Explanation for choice of comparators

This study will adapt and integrate a novel PrEP initiation intervention at point of care in rural SSPs using strengths-based case management (SBCM) approaches to elicit and address structural, environmental and psychosocial barriers to PrEP care. Participants will be randomized into: CDC-PrEP (an in-use PrEP intervention based on CDC guidelines), or the experimental SBCM-PrEP intervention. CDC-PrEP utilizes structured risk assessments and educational materials recommended by the CDC and operates as a point of care model with embedded APRNs providing clinical screening, prescribing, and monitoring of patients in a single session. SBCM-PrEP provides up to 5 strengths-based sessions to deliver tailored PrEP education and engage in action planning to increase readiness for PrEP initiation.

The rationale for the selection of the intervention comparators is threefold:

- 1) use of an active comparator (CDC-PrEP) meets an ethical standard to provide high-risk participants with needed basic education and the potential to access PrEP;
- 2) examination of a brief, in-use content specific intervention for PrEP based on CDC guidelines affords the opportunity to establish preliminary efficacy of an existing intervention that has not been formally tested within the SSP context, and whose brevity may contribute to scalability if efficacious; and
- 3) Comparison with the SBCM-PrEP will examine the value-added of a more robust, but brief, client-driven intervention that supports PrEP initiation through active advocacy to reduce multi-level barriers to uptake.

Objectives	7	Specific objectives or hypotheses
		
The primary objective is to examine preliminary efficacy and effect sizes of the novel SBCM-PrEP and CDC-PrEP interventions on the primary outcome of PrEP initiation (measured by dispensed PrEP prescription) in HIV- participants who inject drugs.

Trial design	8	
Description of trial design including type of trial (eg, parallel group, crossover, factorial, single group), allocation ratio, and framework (eg, superiority, equivalence, noninferiority, exploratory)
 
The trial is designed as a randomized, controlled exploratory trial with two parallel groups and a primary endpoint of PrEP initiation during 3 months after enrollment. Randomization will be stratified by site and gender and performed with a 1:1 allocation.

Methods: Participants, interventions, and outcomes

Study setting	9	Description of study settings (eg, community clinic, academic hospital) and list of countries where data will be collected. Reference to where list of study sites can be obtained
		Rural HIV- PWID will be recruited and sampled from two participating SSP locations in Knox and Clay Counties in rural southeastern Kentucky. Both SSPs are operated by health departments that provide a wide range of health and clinical care and are integrated with other health department services. SSP locations were purposefully selected for inclusion in the study based on their robust operational SSPs serving relatively large numbers of unique clients and location in rural southeastern KY counties that are among the nation's top ten most vulnerable to HIV among PWID.
Eligibility criteria	10	Inclusion and exclusion criteria for participants. If applicable, eligibility criteria for study centres and individuals who will perform the interventions (eg, surgeons, psychotherapists)
		Eligible participants will: 1) be at least 18 years of age; 2) report at least one occasion of injection drug use in the past month; 3) report sharing of injection equipment at least once in the past six months consistent with CDC indications for PrEP; 4) be a documented client of the county SSP at the time of study entry; and, 5) express willingness to participate in a multi-session intervention and follow-up. Exclusion criteria will include: HIV+ status, and current PrEP care.
Interventions	11a	Interventions for each group with sufficient detail to allow replication, including how and when they will be administered
		Participants will be randomized into: CDC-PrEP or the experimental SBCM-PrEP intervention. CDC-PrEP is 1 session PrEP education following CDC guidelines delivered one on one by trained study staff to individual clients in the syringe service program setting. This session will occur within one week of study enrollment. SBCM-PrEP is a multi-session Strengths-Based Case Management intervention adapted for PrEP related educational content delivered one on one by trained study staff to individual clients in the syringe service program setting within one week of enrollment. In both arms, participants interested in starting PrEP are referred to the onsite Advanced Practice Registered Nurse for clinical PrEP screening.
	11b	Criteria for discontinuing or modifying allocated interventions for a given trial participant (eg, drug dose change in response to harms, participant request, or improving/worsening disease)

		-N/A
	11c	Strategies to improve adherence to intervention protocols, and any procedures for monitoring adherence (eg, drug tablet return, laboratory tests)
		Study staff will attempt to contact participants to remind them of intervention session appointments the day before each scheduled session, and participants will be allowed to reschedule missed sessions. In sessions participants will be asked about PrEP adherence, and problems or barriers addressed.
	11d	Relevant concomitant care and interventions that are permitted or prohibited during the trial
		N/A
Outcomes	12	Primary, secondary, and other outcomes, including the specific measurement variable (eg, systolic blood pressure), analysis metric (eg, change from baseline, final value, time to event), method of aggregation (eg, median, proportion), and time point for each outcome. Explanation of the clinical relevance of chosen efficacy and harm outcomes is strongly recommended
		Primary Outcome Measure: Difference between the two intervention arms in the number of participants initiating PrEP at 3 and 6 month follow-up.
		1. Number of participants initiating PrEP Documented PrEP initiation, measured by dispensed PrEP prescription. [Time Frame: 3 months post-baseline]
		2. Number of participants initiating PrEP Documented PrEP initiation, measured by dispensed PrEP prescription. [Time Frame: 6 months post-baseline]
		Secondary Outcome Measures:
		3. Level of Intervention Engagement assessed by session checklist 5 item Session Checklist completed by Nurse-Interventionist post-session; range is 0-15, higher scores are higher engagement

[Time Frame: 8 weeks post-baseline]

4. Level of Intervention Satisfaction assessed by the IAQ

8 item Intervention Acceptability Questionnaire (IAQ) completed by participants post-intervention; range is 0-32, higher scores are higher satisfaction

[Time Frame: 8 weeks post-baseline]

Participant timeline 13 Time schedule of enrolment, interventions (including any run-ins and washouts), assessments, and visits for participants. A schematic diagram is highly recommended (see Figure)

-Figure 1 and Table 1

Sample size 14 Estimated number of participants needed to achieve study objectives and how it was determined, including clinical and statistical assumptions supporting any sample size calculations

The pilot RCT is not designed to establish superiority of the SBCM-PREP, but to generate valid parameter estimates and preliminary evidence of effect sizes for application in a subsequent large trial. The proposed sample size of 80 aligns with recommended sample sizes for two-arm pilot trials structured as planning for subsequent major trials. Assuming a retention rate of 90% at 6 months, there will be 36 participants per intervention group for analysis, which is sufficient.

Recruitment 15 Strategies for achieving adequate participant enrolment to reach target sample size

Recruitment is balanced across the two SSP locations and by gender, targeting enrollment of 40 individuals per location, or 80 in total. Within the SSP settings, potential participants will be screened by research staff on rotating days of the week when the SSPs are operational and eligible participants will be invited to participate. Approximately 6-8 individuals will be enrolled into the study each month across the two sites; challenges meeting the enrollment target based on prior research in these settings and current volumes of SSP clients are not anticipated.

Methods: Assignment of interventions (for controlled trials)

Allocation:

Sequence generation 16a Method of generating the allocation sequence (eg, computer-generated random numbers), and list of any factors for stratification. To reduce predictability of a random sequence, details of any planned restriction (eg, blocking) should be provided in a separate document that is unavailable to those who enroll participants or assign

interventions

Participants will be randomly assigned to either the CDC-PrEP or SBCM-PrEP with a 1:1 allocation per a computer-generated randomization schedule stratified by site and gender.

Allocation concealment mechanism	16b	Mechanism of implementing the allocation sequence (eg, central telephone; sequentially numbered, opaque, sealed envelopes), describing any steps to conceal the sequence until interventions are assigned -The study coordinator and PI are notified of the allocation via secure email.
Implementation	16c	Who will generate the allocation sequence, who will enroll participants, and who will assign participants to interventions -The study Co-I statistician will generate the allocation sequence. The study interviewer will enroll participants, and the study coordinator will assign participants to intervention arms.
Blinding (masking)	17a	Who will be blinded after assignment to interventions (eg, trial participants, care providers, outcome assessors, data analysts), and how -N/A – the study is not blinded
	17b	If blinded, circumstances under which unblinding is permissible, and procedure for revealing a participant's allocated intervention during the trial

Methods: Data collection, management, and analysis

Data collection methods	18a	Plans for assessment and collection of outcome, baseline, and other trial data, including any related processes to promote data quality (eg, duplicate measurements, training of assessors) and a description of study instruments (eg, questionnaires, laboratory tests) along with their reliability and validity, if known. Reference to where data collection forms can be found, if not in the protocol All study staff complete training on study assessments. Primary outcomes include PrEP initiation (measured by dispensed PrEP prescription) 3- and 6- months post-baseline, and acceptability of the intervention (measured by intervention engagement and satisfaction) during the active intervention period. Acceptability will be measured by engagement in the intervention using an interventionist completed session checklist, and a client completed Intervention Acceptability Questionnaire (IAQ) will assess satisfaction.
-------------------------	-----	---

Study instrumentation will collect self-report information on participation in PrEP screening, prescription, and adherence, however, primary measures will be drawn from HD/SSP medical record data to be extracted from the Patient Encounter Form (PEF) and Adult History and Physical Form through chart review at 3-and 6-months post baseline. Data points planned for extraction include: visit date, visit location (including phone or telehealth), provider number, patient ID number, CPT visit type, ICD codes, current medications, laboratory tests conducted relevant to CDC PrEP guidelines (HIV testing, viral hepatitis testing, STI testing, kidney function, and pregnancy testing), and PrEP prescription issuance/refills. For participants who receive a PrEP prescription from the nurse-interventionist, provider-initiated pharmacy verification and/or participant prescription documentation will be used to verify that the prescription was dispensed to the patient.

Well-validated measures will examine participant and risk environment characteristics that may influence intervention outcomes. These measures will be collected at baseline, 3-and 6- month follow-up. The primary data collection instrument contains abbreviated segments of: a. Global Appraisal of Individual Needs (GAIN, v. 5.4) to capture demographics, substance use, physical and mental health, violence, housing situation, transportation; b. Collaborative Injection Drug User Study III/Drug User Intervention Trial Assessment Instrument to capture injection behaviors and equipment sharing, and sources of injecting equipment including SSPs; c. items on secondary syringe exchange, syringe disposal, and syringe coverage, d. Community Stigma related to substance use; and, e. Law Enforcement Activity near or enroute to SSP locations. Validated measures of perceived HIV risk, HIV-related community stigma, PrEP awareness, acceptability, and use, dignity denial, and PrEP adherence at follow-up have been included.

18b Plans to promote participant retention and complete follow-up, including list of any outcome data to be collected for participants who discontinue or deviate from intervention protocols

Participants will be located for follow-up using detailed locator information collected at baseline. Project staff will also have a routine presence in the SSPs to maintain ongoing contact with participants. Participants will receive a \$25 payment for data collection and transportation costs at 3-month and 6-month follow-up.

Data management

19 Plans for data entry, coding, security, and storage, including any related processes to promote data quality (eg, double data entry;

range checks for data values). Reference to where details of data management procedures can be found, if not in the protocol

Interview data will be collected at two remote SSP sites on a laptop interface through a REDCap survey application, which is housed on secure servers at UK. The application will provide the technical functionality required to remotely collect interview data and ensure data security during transmission to UK. Branching logic and range checks for data values are built into the REDCap assessments to promote data quality. The interview dataset will be audited for quality control issues on a bi-weekly basis.

Statistical methods	
20a Statistical methods for analysing primary and secondary outcomes. Reference to where other details of the statistical analysis plan can be found, if not in the protocol
 
A total of 80 HIV- rural PWID will be randomly assigned to the two intervention groups. The major interest in Specific Aim 3 is to evaluate the preliminary efficacy of the intervention conditions on PrEP initiation (measured by dispensed PrEP prescription) at 3- and 6-month follow-ups. With 36 participants per intervention condition, and utilizing a 95% confidence interval, we will be able to estimate the true probability of PrEP initiation for either trial arm within a maximum of ± 0.16. To address Aim 3, robust analytic methods will be used for descriptive purposes and data analyses. Descriptive statistics (e.g., frequencies, proportions, means, and standard deviations) will be used to describe process variables (e.g., the number of sessions attended, engagement scores). Bivariable analyses will be used to examine potential differences in feasibility and acceptability between the two study conditions. Conventional statistical methods, such as t-tests, Chi- square, ANOVA, ANCOVA, OLS, and logistic regression will be used for preliminary analyses of the demographic and risk environment characteristics of PWID, as well as those associated with PrEP initiation. Tests will be two-sided at the 0.05 level. Similarly, to examine initiation of PrEP, as well as continuation of PrEP among those who initiated by 3 months, we will utilize frequencies, proportions, and corresponding 95% confidence intervals. Additionally, logistic regression models will be utilized to assess for group differences, adjusting for site due to its use as a stratification factor.
 
20b Methods for any additional analyses (eg, subgroup and adjusted analyses)
 
N/A
 
20c Definition of analysis population relating to protocol non-adherence (eg, as randomised analysis), and any statistical methods to handle

---------------------	---

missing data (eg, multiple imputation)

We will use an intent-to-treat approach, analyzing data from all participants based on the trial arms to which they were randomized regardless of whether they receive or complete the randomized treatment to which they were assigned.

Analysis of the primary outcome (PrEP initiation) should not be affected by patient withdrawals or loss to follow up, as we will have process and medical records data to document for each participant whether they had an initial meeting with the nurse practitioner and whether a PrEP prescription was issued.

Analyses of secondary outcomes will utilize all available data.

Multiple imputation of missing data may be considered for sensitivity analyses.

Methods: Monitoring

Data monitoring 21a

Composition of data monitoring committee (DMC); summary of its role and reporting structure; statement of whether it is independent from the sponsor and competing interests; and reference to where further details about its charter can be found, if not in the protocol.

Alternatively, an explanation of why a DMC is not needed

A Data and Safety Monitoring Board has been established including the following members: [name]. (chair), [name]. (member), and [name] (member). The DSMB is independent of the study organizers. The DSMB will meet before the trial is fielded to review the initial protocol elements. During the period of study enrollment the DSMB will hold regular meetings every 6 months to evaluate the progress, safety and efficacy of the trial:

- i. Admission data, including eligibility data, the participant flow chart, retention, and overall progress toward targeted goals.
- ii. Protocol compliance, including quality assurance reports and protocol deviations and violations
- iii. Human subjects safety reports, including individual SAEs (identity data removed) and aggregated, categorized AEs.
- iv. Aggregated efficacy data by study arm, including all outcome measures. The Chair of the DSMB may request special data reports in any format and at any time.
- v. Actions taken in response to prior recommendations of the DSMB.
- vi. Compliance with reporting of SAEs and AEs to the IRB and to NIDA as described in the DSMP.

21b Description of any interim analyses and stopping guidelines, including who will have access to these interim results and make the final decision to terminate the trial

		The DSMB will independently make recommendations to researchers to continue, amend or terminate the trial based on the interim analysis of the safety data, efficacy data, and/or performance data (e.g., protocol violations, improper entry criteria, slow accrual rate, low participation rate, failure of randomization, inadequate treatment adherence, inadequate follow-up rate, severely compromised validity) and to independently make recommendations for improvement or termination if the trial would be unable to prove anything meaningful, regardless of modifications.
Harms	22	Plans for collecting, assessing, reporting, and managing solicited and spontaneously reported adverse events and other unintended effects of trial interventions or trial conduct
		Adverse events (AEs) are collected and assessed at each study visit. AEs are summarized in regular reporting to the DSMB, and annual reports to the IRB and NIDA. Prompt reporting guidelines to NIDA, the IRB, and the DSMB regarding Serious Adverse Events are followed.
Auditing	23	Frequency and procedures for auditing trial conduct, if any, and whether the process will be independent from investigators and the sponsor
		The study statistician does audits of the trial conduct and the PI or study coordinator will verify that the study assessments are completed on schedule. Results are shared with the investigator team.
Ethics and dissemination		
Research ethics approval	24	Plans for seeking research ethics committee/institutional review board (REC/IRB) approval
		Approval obtained from:
		Board Name: (Medical) Institutional Review Board
		Board Affiliation: University of Kentucky
		[contact] Email: [contact]
		Address:
		Office of Research Integrity
		University of Kentucky
		[name]
		[name]
Protocol amendments	25	Plans for communicating important protocol modifications (eg, changes to eligibility criteria, outcomes, analyses) to relevant parties (eg, investigators, REC/IRBs, trial participants, trial registries, journals, regulators)

		NIDA, the IRB and DSMB will be informed of all protocol modifications on an ongoing basis.
Consent or assent	26a	
Who will obtain informed consent or assent from potential trial participants or authorised surrogates, and how (see Item 32)
 
-Trained and approved study staff who have completed required human subjects protection trainings will obtain informed consent.

	26b	Additional consent provisions for collection and use of participant data and biological specimens in ancillary studies, if applicable
		N/A
Confidentiality	27	
How personal information about potential and enrolled participants will be collected, shared, and maintained in order to protect confidentiality before, during, and after the trial
 
Participants receive a unique identifier, and all PHI is stored separately. Data are stripped of all PHI prior to analysis, and all reports are of the de-identified, aggregate data.

Declaration of interests	28	
Financial and other competing interests for principal investigators for the overall trial and each study site
 
The investigators have no competing interests

Access to data	29	
Statement of who will have access to the final trial dataset, and disclosure of contractual agreements that limit such access for investigators
 
There are no contractual agreements limiting investigators access to the final trial dataset.

Ancillary and post-trial care	30	
Provisions, if any, for ancillary and post-trial care, and for compensation to those who suffer harm from trial participation
 
-For PrEP care, participants will receive a referral for ongoing care elsewhere.

Dissemination policy	31a	
Plans for investigators and sponsor to communicate trial results to participants, healthcare professionals, the public, and other relevant groups (eg, via publication, reporting in results databases, or other data sharing arrangements), including any publication restrictions
 
-The investigators plan to present results to the study sites, at national conferences and to publish study results

31b Authorship eligibility guidelines and any intended use of professional writers
-No plan for professional hired writers

31c Plans, if any, for granting public access to the full protocol, participant-level dataset, and statistical code
-N/A at this time

Appendices

Informed consent materials 32 Model consent form and other related documentation given to participants and authorised surrogates
Stamped and approved study consent form is attached.

Biological specimens 33 Plans for collection, laboratory evaluation, and storage of biological specimens for genetic or molecular analysis in the current trial and for future use in ancillary studies, if applicable
N/A

STATISTICAL DESIGN AND POWER: PWID

Aim 3 Analytic Plan and Sample Size Considerations. The overarching goal of this R34 is to adapt and feasibility test an evidence-based SBCM intervention, and examine preliminary efficacy of the intervention comparators (SBCM-PrEP and CDC-PrEP). Within this context, our Aim 3 pilot RCT is not designed to establish superiority of the SBCM-PrEP, but to evaluate feasibility of our procedures and implementation processes, examine acceptability of methods, intervention content and format, to generate valid parameter estimates and preliminary evidence of effect sizes for application in a subsequent R01, which are preferred endpoints for many pilot trials. The proposed sample size of 80 aligns with rules of thumb and recommended sample sizes for two-arm pilot trials structured as planning for subsequent major trials. Assuming a retention rate of 90% at 6 months, there will be 36 participants per intervention group for analysis, which is sufficient for the Aim 3 pilot.

Precision Analysis. A total of 80 HIV- rural PWID will be randomly assigned into the two intervention groups. The major interest related to Specific Aim 3 is to evaluate the preliminary efficacy of the intervention conditions on the primary study outcome (PrEP initiation, measured by dispensed PrEP prescription) at 3- and 6- month follow-ups. With 36 participants per intervention condition, and utilizing a 95% confidence interval, we will be able to estimate the true probability of PrEP initiation for either trial arm within a maximum of ± 0.16 .

To address Aim 3, robust analytic methods will be used for descriptive purposes and data analyses. Descriptive statistics (e.g., frequencies, proportions, means, and standard deviations) will be used to describe targeted process variables (e.g., proportion of women agreeing to enroll in the study, the number of sessions attended, engagement scores, etc.). Bivariable analyses will be used to examine potential differences in feasibility and acceptability between the two study conditions. Conventional statistical methods, such as t-tests, Chi-square, ANOVA, ANCOVA, OLS, and logistic regression will be used for preliminary analyses of the demographic and risk environment characteristics of PWID, as well as those associated with PrEP initiation. Tests will be two-sided at the 0.05 level. Similarly, to examine initiation of PrEP, as well as continuation of PrEP among those who initiated by 3 months, we will utilize frequencies, proportions, and corresponding 95% confidence intervals. Additionally, logistic regression models will be utilized to assess for group differences, adjusting for site due to its use as a stratification factor.

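### The stated objective claims preliminary efficacy for both SBCM-PrEP and CDC-PrEP, but the two-active-arm design identifies only the effect of one relative to the other

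*Combined protocol and SAP*

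**What the plan says.** The efficacy claim for both interventions appears in three places.

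- Item 7 (Objectives): "The primary objective is to examine preliminary efficacy and effect sizes of the novel SBCM-PrEP and CDC-PrEP interventions on the primary outcome".
- Item 6b (choice of comparators), second reason: testing CDC-PrEP "affords the opportunity to establish preliminary efficacy of an existing intervention that has not been formally tested within the SSP context". The third reason, the added value of SBCM-PrEP over CDC-PrEP, is listed separately, so the second is a claim about CDC-PrEP in its own right.
- Aim 3 Analytic Plan and Sample Size Considerations: the project will "examine preliminary efficacy of the intervention comparators (SBCM-PrEP and CDC-PrEP".

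On design, item 8 says "The trial is designed as a randomized, controlled exploratory trial with two parallel groups", and item 6b says "Participants will be randomized into: CDC-PrEP (an in-use PrEP intervention based on CDC guidelines), or the experimental SBCM-PrEP intervention". No other arm or external control is described.

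The documents describe the nurse's role in two ways. Item 6b presents CDC-PrEP as a point-of-care model with nurses embedded in it who screen, prescribe and monitor. Item 11a describes CDC-PrEP as a single education session and then adds: "In both arms, participants interested in starting PrEP are referred to the onsite Advanced Practice Registered Nurse for clinical PrEP screening".

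Item 12 defines the primary outcome measure as the difference between arms in the number initiating PrEP at 3 and 6 months. Item 20a and the SAP plan proportions with 95% confidence intervals and a site-adjusted logistic regression for group differences. They give one precision figure: ±0.16 for the initiation probability in either arm.

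**The concern.** An effect size is a contrast, and two active arms supply one randomised contrast. The proportion initiating under CDC-PrEP is an outcome level. It becomes an effect only when set against what the same people would have done without CDC-PrEP, and the plan neither observes nor assumes that quantity.

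Two things are at stake. The first is the conclusion. If initiation is similar in both arms, the objective as worded leaves room to say that both interventions showed preliminary efficacy. The data would fit equally well with neither having any effect against its absence. The second is the use of the results. The pilot exists to supply effect sizes for a later, larger trial. The plan states an efficacy aim and follows it with the precision of a single-arm proportion, so whoever plans that trial could take an arm's initiation proportion for an effect.

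**Working it through.** **Inputs.** 80 randomised 1:1 (items 8 and 14); 90% retention at 6 months (item 14); 95% intervals and a stated maximum of ±0.16 for one arm (item 20a and Precision Analysis).

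**1. Reproducing the plan's figure.** Analysed per arm: 80 × 0.90 / 2 = 36. Maximum Wald half-width for one proportion, at p = 0.5: 1.96 × √(0.25/36) = 0.163, which rounds to the stated 0.16. (Wilson gives 0.155 and Clopper-Pearson 0.171.) The figure is sound as the precision of one arm's proportion.

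**2. Precision of the effect that is identified.** For SBCM-PrEP minus CDC-PrEP, the unadjusted maximum half-width with both proportions at 0.5 is 1.96 × √(2 × 0.25/36) = 0.231. This is √2 times the single-arm value. If all 40 per arm are analysed, as the records-based approach in item 20c would allow, it is 1.96 × √(2 × 0.25/40) = 0.219. If initiation is 0.20 in both arms (an assumed value), the half-widths at 36 per arm are:

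- one arm: 1.96 × √(0.16/36) = 0.131
- difference: 1.96 × √(2 × 0.16/36) = 0.185

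**3. What is not identified.** The effect of CDC-PrEP against its absence is p(CDC-PrEP) − p(without CDC-PrEP). The meaning of the second term depends on how CDC-PrEP is defined:

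| Reading | Source | Counterfactual needed | Observed? |
|---|---|---|---|
| Nurse prescribing is part of CDC-PrEP | Item 6b | SSP care without co-located PrEP | No |
| Nurse referral is a pathway shared by both arms | Item 11a | Onsite nurse access without the education session | No |

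The term is missing on either reading. The same holds for SBCM-PrEP, for which only the increment over CDC-PrEP is available.

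**4. Illustration with assumed values.** Suppose 0.20 initiate under CDC-PrEP.

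| Assumed background initiation | Implied effect of CDC-PrEP |
|---|---|
| 0 | 0.20 |
| 0.05 | 0.15 |
| 0.10 | 0.10 |
| 0.20 | 0 |

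The documents give no background rate with which to choose a row. This uncertainty comes on top of sampling error and does not shrink as the sample grows.

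**The case against.** The strongest defence is that the plan is already comparative where it matters. Item 12 defines the primary outcome measure as a between-arm difference, the planned regression tests group differences, and no analysis tests either arm against zero or a benchmark. The trial is labelled exploratory, item 14 says it is not designed to establish superiority, and efficacy is called preliminary throughout. The comparator also has a stated justification: "use of an active comparator (CDC-PrEP) meets an ethical standard".

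Most of this stands. It shows that the analysis is largely right and that the fault lies in the claim. But the word preliminary qualifies how certain an estimate is; it cannot supply a counterfactual that the design lacks. Nor does a comparative outcome measure support the second reason in item 6b.

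A further defence is that background uptake must be near nil. People in current PrEP care are excluded, and the background section describes scarce providers and low PrEP knowledge. If CDC-PrEP includes the nurse, this makes a high background rate unlikely. It does not give a rate: the exclusion fixes status at entry, not initiation over the next 3 to 6 months. If the nurse pathway is instead shared, those arguments say little about uptake with a prescriber on site.

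A reader might also infer that nurse prescribing contaminates the CDC-PrEP arm. The documents do not support that as a flat statement, because item 6b describes the nurse as part of the CDC-PrEP model. The point here does not depend on which description is used.

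**Conclusion.** The concern holds as a mismatch between the stated objective and what the design identifies. Randomisation identifies SBCM-PrEP versus CDC-PrEP, with a maximum 95% half-width of about 0.23 at 36 per arm (0.22 at 40). It does not identify the effect of either intervention against its absence. This rests on the absence from the documents of any usual-care, waitlist, historical or pre-period control and of any background rate. The half-widths are unadjusted Wald values at proportions of 0.5.

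Three stronger readings should be resisted.

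- A reader might infer that the trial can estimate no effect involving CDC-PrEP. It can: the relative effect is estimable, and the third reason in item 6b is supported.
- A reader might infer that an untreated arm is required. The active comparator is justified on ethical grounds, and the planned contrast is a legitimate one.
- A reader might infer that the team intends to declare both interventions efficacious. No planned analysis does so; the wording of the objective merely leaves room for it.

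The range in the illustration depends on assumed values and is not an estimate for this trial.

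**What to change.** In items 6b, 7 and 20a and the matching SAP text:

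1. Remove the claim that the trial establishes preliminary efficacy of CDC-PrEP, and reword the objective so that efficacy and effect size refer to SBCM-PrEP relative to CDC-PrEP.
2. Keep the planned arm-specific initiation proportions with 95% CIs, and label them as descriptive.
3. Name the SBCM-PrEP minus CDC-PrEP difference in the proportion initiating, with a 95% CI, as the effect size. The site-adjusted logistic regression can stay alongside it.
4. State the precision of that difference (maximum half-width about 0.23 at 36 per arm) next to the single-arm 0.16.

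The cost is a slightly less favourable claim and a wider stated precision. Arms, allocation, sample size, visits and data collection do not change. Most of the analysis is already planned; the new elements are the CI for the difference, its stated precision and the descriptive label.
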